1.0 BACKGROUND

Pelvic floor dysfunction (PFD), disproportionately affecting older women, involves loss of pelvic floor support and urinary and fecal incontinence. Medical options are limited and up to 11% of women will require surgery, with increasing risk due to surgery with advancing age. The cause of PFD is multifactorial and complex, and although risk factors are known, precise mechanisms are yet to be elucidated. Our primary aim in the current proposal is to determine important tissue differences, including muscle and connective tissue changes, between postmenopausal women and reproductive age women with PFD to help develop targeted treatments. In addition, we propose to develop noninvasive methods to evaluate future treatments for PFD. These goals will be complementary to provide preliminary data for submission for NIH funding for preclinical or clinical (FDA approved drugs) studies of potential medical treatments for PFD.

A. Significance

A1. PFD is increased in aging women.

Pelvic floor dysfunction affects up to 50% of elderly women._{1,2} Pelvic floor function involves the interplay between muscles, nerves and connective tissue, and dysfunction results in pelvic organ prolapse, urinary complaints (incontinence and voiding disorders) and defecatory dysfunction (constipation, incomplete emptying, and fecal incontinence). In addition to the discomfort of this medical condition, falls and fractures are more common in women with PFD,7 suggestive that a sarcopenic condition is present. Psychosocial dysfunction, including depression and isolation are more common in women with this socially embarrassing disorder.₈

Current treatments for PFD include pelvic floor muscle exercise and topical estrogen. However, most symptomatic women present with advanced cases of pelvic organ prolapse where pessary (vaginal support device) and surgery are the only options for relief of symptoms. Some types of prolapse are not responsive to pessary use or women may not be comfortable with the use of this device, therefore surgical management is common for treatment of PFD, with an 11% lifetime risk of surgery.9,10 Unfortunately, recurrence of prolapse after surgical management is common,11,12 and surgical risks are increased in older women. Women undergoing urogynecologic procedures after the age of 80 have a 13.6 times increased risk of death after the procedure compared with their younger counterparts.13 Thus, one goal of this project is to identify the inflammatory and pelvic tissue metabolic dysregulation that occurs with PFD to better identify targeted nonsurgical treatment options for symptom relief in older women with limited treatment options.

A2. Multi-factorial cause of PFD

Because pelvic floor support depends on a complex interplay of factors, the cause of PFD is multifactorial. Three proven risk factors for the development of this common disorder have been identified and include vaginal delivery, obesity, and age. 14-16 Since normal aging also induces wasting of the limb muscles, and vaginal and pelvic floor atrophy is commonly seen in PFD, we surmised that similar inducers of sarcopenia (loss of hormones, diminished blood flow, and inflammation) may be influencing PFD in older women along with other known factors listed below.

Tissue Injury from childbirth and pregnancy as precipitating factor - Mechanical injury to the pelvic floor is the precipitating factor for PFD, beginning in the reproductive years, with multiple births and

delivery of large babies increasing this risk._{17,18} In addition, continued mechanical stress on the pelvic floor, including chronic cough or chronic straining in constipation, increases the risk for PFD.

Hormonal Effects on Tissue - The most dramatic aging effects on the health of the vaginal wall and support structures occurs at the time of menopause, coinciding with an increase in symptomatic PFD. While vaginal estrogen use may assist some women with urinary urgency, recent data shows that it is not a successful treatment for urinary incontinence and prolapse. Additionally, the vaginal estrogen response is blunted in chronically estrogen-deprived cells. Estrogen is not an option for all women due to breast cancer or fear of estrogen supplementation.

The impact of progesterone and testosterone deprivation and supplementation on the health of pelvic support has not been well studied. Treatment of rats with testosterone improved urinary incontinence, presumably due to anabolic effects on the supportive pelvic floor muscles.₂₁ However, testosterone supplementation in ovariectomized (simulating menopause) mice has shown thinned vaginal epithelium, therefore further study of testosterone's effects on the entire pelvic floor should be studied.₂₂

Muscle atrophy - Loss of pelvic floor support and muscular tone plays a critical role in PFD. Age has been associated with decreased pelvic floor muscle strength and increased size of the levator hiatus.₂₃ Women with PFD have decreased muscle contraction and tone in the levator ani muscles. Pelvic floor physical therapy, including biofeedback and Kegel exercises are helpful in improving mild urinary incontinence. A study in surgical patients showed 74% degeneration of striated muscles in levator ani muscles of women with urinary incontinence when compared with controls (0%).₂₄ Dysregulation of the vaginal smooth muscle content has an age dependent effect in women with pelvic organ prolapse.₂₅

Vasculature - Decreased hormonal influence on the vagina and reproductive organs from lack of estrogen after menopause leads to decreased blood flow to pelvic organ structures including the uterus and vagina. This decreased blood flow, which can be observed during a vaginal exam and appears white and avascular in nature, can also be easily measured with ultrasound by our group, and may play a role in the atrophy of the uterus and vagina occurring after menopause; similar to the role skeletal muscle perfusion plays in age-related sarcopenia.₂₂ Testosterone may independently play a role in blood flow to the vagina.₂₆ A study of ovariectomized rats showed normalization of vaginal blood flow after treatment with testosterone.₂₇

Elastin and Collagen Structure - Women with PFD have been noted to have a vaginal connective tissue balance shifted toward *degradation* rather than *regeneration* as compared to women without prolapse. Animal studies show increased matrix metalloproteinases MMPs (proteins which break down connective tissue elements) and abnormal collagen/elastin in a mouse model of prolapse, with few confirmatory human studies.₆

Inflammation may play a role in the development of PFD - Two of the three major risk factors for PFD, age and obesity, are associated with inflammatory changes of the pelvic wall tissue. Additionally, postmenopausal women are more likely to have atrophic vaginitis related to decreased hormones and epithelial barrier function.₂₈ The pH and vaginal microflora change, increasing the risk of infection and further inflammation. The role of inflammation in the development of PFD has not been well studied,

though increased inflammation and resulting elevated MMPs is thought to effect the support of the pelvic organs._{5,6} Determining the important factors in development of PFD will allow us to strategize for optimal medical management of this disease and to target reversible tissue changes before they become permanent.

A3. Scientific innovation to improve health

We will utilize knowledge gained from this proposal in humans to direct future research projects to test targeted topical treatments in a mouse model of PFD and then translate these targeted treatments to clinical research.

Our long term goal is to develop drug combinations to be delivered topically (e.g. intravaginal rings). Finally, further refining of our pelvic imaging techniques to noninvasively monitor pelvic floor health would greatly improve our ability to individualize treatment of women with PFD and to monitor them after treatment and for early signs of progression of disease.

2.0 Rationale and Specific Aims

Aim: To determine the effect of aging, vaginal wall inflammatory markers, and macro- and microcirculatory flow on PFD.

- 1. Full thickness vaginal wall specimens and vaginal fluid collected during surgery will be evaluated for the primary outcome of tissue inflammatory cytokines.
- 2. Secondary outcomes will include evaluation of tissue MMPs, collagen/elastin structure, microvasculature, and muscle thickness.
- 3. To evaluate macrocirculatory blood flow in pelvic organs, women will be assessed with noninvasive imaging before and after randomization to vaginal estrogen in the postmenopausal group in the perioperative period.
- 4. Microcirculation will be measured by histologic staining of tissue vasculature

Data from this project will increase our understanding of the mechanisms of loss of pelvic floor muscle support, identify therapeutic targets and improve our ability to medically treat women with PFD, providing a safer, nonsurgical, and noninvasive option of diagnosis and treatment, and providing the necessary preliminary data for a NIH grant application.

We propose a 1-month peri-operative study in older women with PFD to assess inflammatory markers and blood flow in pelvic wall tissues. Younger women with PFD will serve as a positive control.

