3.0 Study Population and Inclusion/Exclusion

It is anticipated that up to 30 female patients with Stage II or greater pelvic organ prolapse with planned gynecologic surgery at UTMB will be involved in this study with at least 15 participants completing the study, including at least 10 postmenopausal women, and at least 5 reproductive age women. Patients planning surgery for Stage II or greater pelvic organ prolapse may be eligible to participate. The study team will provide information about the study, including inclusion and exclusion, to clinic providers who may then inform their eligible patients about the study. If interested in learning more about the study, patients will be asked to speak with a study team member. The informed consent process will be completed in the clinic with a study team member authorized to

obtain study consent. During the consent process, patients are reminded of the voluntary nature of research participation; patients wanting to take part in the study are asked to sign the current approved study consent form. The completed written study consent form must be on file prior to a patient's participation in any study procedure.

Subjects must meet all of the inclusion criteria in order to participate in the study.

Inclusion criteria are:

- Females, 21 to 70 years of age, at the time of consent.
- Stage II or greater pelvic organ prolapse.
- Individuals who desire surgery to treat their PFD.
- Willing and able to comply with study procedures.
- Willing and able to provide written informed consent.

Subjects meeting any of the exclusion criteria at baseline will be excluded from study participation.

Exclusion Criteria are:

- Contraindication for estrogen use.
- Any medical condition that, in the opinion of the investigator, would place the subject at increased risk for participation.
- History of connective tissue disease
- Previous hysterectomy or pelvic organ prolapse surgery.
- Known allergic reaction to any agent under investigation or required by the protocol.
- Use of hormone therapy in postmenopausal women within the last 90 days.
- History of prior non-compliance or the presence or history of psychiatric condition (including drug or alcohol addiction) that would, in the opinion of the investigator, make it difficult for the subject to comply with the study procedures or follow the investigators instructions.
- Females who are pregnant or lactating.

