9.0 Study Withdrawal/Discontinuation

A study subject will be discontinued from participation in the study if any of the following occur:

- Unacceptable toxicity or serious adverse event
- Intercurrent illness, or other medical condition or situation occurs such that continued
 participation in the study would not be in the best interest of the subject in the opinion of the
 treating investigator
- Development of any exclusion criteria
- Subject withdrawals consent to continue in the research for any reason
- Vaginal bleeding of postmenopausal women on treatment cream

Handling of Withdrawals

Subjects who are agreeable may either undergo an exam and exit interview or complete the study procedures as previously described and completed in Study Visit 1 at the time of withdrawal from the study.

If a subject withdraws, a replacement subject may be recruited.

10. Statistical Considerations

This study will be a placebo-controlled, single center study with 3 arms of women planning on undergoing surgery for pelvic organ prolapse.

The primary outcome will be vaginal epithelial thickness based on OCT measures. Findings of collagen and elastin scores, epithelial/stromal/muscularis thickness, cytokines, MMPs, inflammatory cells, and receptors will be also compared between groups. Appropriate statistical analysis for ordinal (e.g. scores) and continuous (e.g. thickness) data will be applied, including tests to determine normality (Shapiro-Wilk) and analysis with ANOVA if criteria are met (e.g. normal, continuous). If ANOVA criteria are not met, then Kruskal-Wallis will be performed for non-normal, ordinal (e.g. scores) data sets.

Power Analysis

Preliminary and historical data are available for OCT thickness, therefore power analysis was based on differences in the OCT thickness mean difference between groups of 40 micrometers with standard deviation 18, and 80% power. Based on T-test and Bonferonni correction (alpha/number of tests = 0.025) for 2 comparisons (1. postmenopausal treatment vs placebo and 2. reproductive age women at 2 different stages of the cycle), five subjects were calculated to be needed per arm to be able to reject

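### Sections 2 and 10 name different primary outcomes (tissue cytokines and OCT epithelial thickness), nothing says which governs, and only OCT has a sample-size basis

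*Combined protocol and SAP*

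**What the plan says.** Section 2.0 (Rationale and Specific Aims), item 1, says that vaginal wall specimens and vaginal fluid taken at surgery "will be evaluated for the primary outcome of tissue inflammatory cytokines". Item 2 lists the secondary outcomes: MMPs, collagen and elastin, microvasculature and muscle thickness. OCT epithelial thickness is in neither item. The one imaging item, item 3, has a different purpose: "To evaluate macrocirculatory blood flow in pelvic organs, women will be assessed with noninvasive imaging before and after randomization".

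Section 10 (Statistical Considerations) says "The primary outcome will be vaginal epithelial thickness based on OCT measures". It then lists further findings, ending with "cytokines, MMPs, inflammatory cells, and receptors will be also compared between groups". Under Power Analysis, it explains that earlier OCT data exist and that for this reason the "power analysis was based on differences in the OCT thickness mean difference between groups of 40 micrometers with standard deviation 18". The Bonferroni level of 0.025 covers two comparisons: estrogen versus placebo in postmenopausal women, and "reproductive age women at 2 different stages of the cycle". The result is five women per arm.

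Section 3.0 foresees "up to 30 female patients", with "at least 15 participants completing the study, including at least 10 postmenopausal women, and at least 5 reproductive age women". Section 4.0 divides them into three groups of about equal size.

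**The concern.** Each section speaks of the primary outcome in the singular, so the two statements do not read as co-primaries. The two rankings conflict: Section 2.0 puts cytokines first and omits OCT thickness, while Section 10 puts OCT thickness first and cytokines among the rest. No passage gives one section precedence.

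Three things are at stake.

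- **Selective reporting.** An author could call either result primary once both are known, and cite the plan for it.
- **Error control.** The 0.025 level was set for two comparisons in the OCT power analysis. It makes no allowance for a second primary outcome.
- **Interpretability.** If cytokines are primary, the trial has no stated basis for its size on that outcome, and a null result could not be told apart from lack of power.

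**Working it through.** **1. The two sections side by side**

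| | Section 2.0 | Section 10 |
|---|---|---|
| Primary | Tissue inflammatory cytokines | OCT vaginal epithelial thickness |
| Place of the other outcome | OCT thickness not listed | Cytokines among further findings |
| Difference, SD, alpha, n | None | OCT only: 40 micrometers, 18, 0.025, 5 per arm |

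**2. The plan's own figure**

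Inputs from Section 10: difference 40, SD 18, power 80%, alpha 0.05/2 = 0.025. Sidedness is not stated.

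- Normal approximation, two-sided: n = 2 × [18 × (2.241 + 0.842)/40]² = 3.85, so 4 per arm.
- Noncentral t, two independent groups, two-sided: standardized difference 40/18 = 2.22; noncentrality 2.22 × √(5/2) = 3.51; 8 df; critical value 2.752. Power at 5 per arm is 0.76, and at 6 per arm 0.87.
- One-sided 0.025: power 0.75 at 4 and 0.87 at 5, so exactly 5.
- Paired t with 18 taken as the SD of differences, two-sided 0.025: power 0.64 at 4 and 0.86 at 5, so exactly 5.

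Five per arm is therefore a recognizable result of the OCT inputs. There is no cytokine calculation to reproduce.

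**3. What the same numbers of women give for a cytokine**

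The plan states no cytokine effect or SD, so differences are assumed in SD units. The comparison is estrogen versus placebo by two-sided t-test; the test and the 0.025 level are borrowed from the OCT power analysis, and 0.05 is also shown. The smallest planned group is 15/3 = 5 completers. The largest, if all 30 women complete in equal groups, is 30/3 = 10.

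Power = P(|T| > t critical), with T noncentral t, df = 2n − 2 and noncentrality d × √(n/2). Example: d = 1.0, n = 5, noncentrality 1.58, critical value 2.752, power 0.185.

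| Alpha | n per arm | 0.8 SD | 1.0 SD | 1.5 SD | 2.0 SD |
|---|---|---|---|---|---|
| 0.025 | 5 | 0.123 | 0.185 | 0.406 | 0.662 |
| 0.025 | 10 | 0.282 | 0.436 | 0.809 | 0.972 |
| 0.05 | 5 | 0.201 | 0.286 | 0.549 | 0.791 |
| 0.05 | 10 | 0.395 | 0.562 | 0.887 | 0.988 |

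At 0.025, 80% power needs a difference of about 2.33 SD at 5 per arm, or 1.48 SD at 10 per arm.

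**4. Whether cytokines fit the rest of the plan as a primary outcome**

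- *Measure and specimen.* Section 2.0 speaks of tissue cytokines. In Section 5.0 the named cytokines (IL-6, TNF-α, TNF-β) are assayed in secretions and lavage. The tissue analysis covers histology, IHC for MMPs, hormone receptors and macrophages, and the transcriptome, but names no tissue cytokine assay. No lead marker is chosen.
- *Timing.* Tissue and fluid are collected once, at surgery. The cycle-phase comparison in Section 10 therefore cannot be made within women for cytokines. OCT can supply it, because it is done at Visits 1 and 2, which are set in opposite phases.

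**The case against.** The strongest reply is that Section 10 is the only statistical section. It says outright that OCT thickness is primary, places cytokines among the other findings and sizes the trial on OCT, so a sensible reader would take it as governing the analysis. That inference is fair, but the plan does not state it. The reason given for powering on OCT is that data were available, which explains the choice of power variable without demoting cytokines. The Aim in Section 2.0 names inflammatory markers and blood flow and does not mention epithelial thickness, so the cytokine designation is not plainly a slip.

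Several narrower points stand as limits on the argument:

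- The power figures illustrate a consequence and do not measure the contradiction. The effects are assumed; with 2.0 SD, power at 0.025 is 66% to 97%.
- Section 10 does give a generic analysis for cytokines (ANOVA or Kruskal-Wallis). What is missing is the sample-size basis, not every analysis rule.
- The cycle-phase comparison is stated only in the OCT power analysis. Its failure for cytokines matters only if they become primary.
- Tissue is also frozen for later analysis, and the transcriptome could include cytokine transcripts. Tissue cytokines may be measurable; the plan just does not say how.

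The trial is also small and meant to supply preliminary data for a grant. That lowers the stakes, but a study that states a primary outcome, alpha and power still has to say which outcome they belong to.

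**Conclusion.** The concern holds. The plan names two different primary outcomes in current text, no passage settles which governs, and only one of the two has a sample-size basis. This rests on the wording alone and needs no assumption.

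The size of the consequence for cytokines does depend on assumptions. For differences of 0.8 to 1.5 SD tested two-sided at 0.025, power runs from about 12% to 41% at the planned minimum of 5 per arm, and from about 28% to 81% at 10 per arm. At 0.05 the ranges are about 20% to 55% and 40% to 89%.

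Correction is required because the primary outcome is a rule on which the trial's conclusion depends, and the choice is credible only if made before results are known.

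**What to change.** Make Sections 2.0 and 10 name the same single primary outcome.

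**Default: OCT vaginal epithelial thickness**, as the only outcome with a sample-size basis. In Section 2.0, state it as primary and move cytokines from item 1 to the secondary outcomes. Section 10 stays as it is on this point and no new data are needed. The cost is that cytokines lose primary status although the Aim centres on inflammatory markers; since Section 2.0 does not mention epithelial thickness, the wording of the Aim should be checked in the same amendment.

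**Alternative: keep cytokines primary.** Both sections must then name one cytokine measure, one specimen and one assay, say that 5 per arm and the two-comparison alpha split were not derived for it, and drop the cycle-phase comparison for that outcome. A sample-size justification would need an assumed effect and SD that the plan does not have.

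Neither option settles a separate question: 5 per arm gives about 76% power for OCT, not 80%, if the test is a two-sided independent-groups t-test at 0.025 for a 40 micrometer difference. Section 10 should state the sidedness and whether the test is paired.

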3.0 Study Population and Inclusion/Exclusion

It is anticipated that up to 30 female patients with Stage II or greater pelvic organ prolapse with planned gynecologic surgery at UTMB will be involved in this study with at least 15 participants completing the study, including at least 10 postmenopausal women, and at least 5 reproductive age women. Patients planning surgery for Stage II or greater pelvic organ prolapse may be eligible to participate. The study team will provide information about the study, including inclusion and exclusion, to clinic providers who may then inform their eligible patients about the study. If interested in learning more about the study, patients will be asked to speak with a study team member. The informed consent process will be completed in the clinic with a study team member authorized to

obtain study consent. During the consent process, patients are reminded of the voluntary nature of research participation; patients wanting to take part in the study are asked to sign the current approved study consent form. The completed written study consent form must be on file prior to a patient's participation in any study procedure.

Subjects must meet all of the inclusion criteria in order to participate in the study.

Inclusion criteria are:

- Females, 21 to 70 years of age, at the time of consent.
- Stage II or greater pelvic organ prolapse.
- Individuals who desire surgery to treat their PFD.
- Willing and able to comply with study procedures.
- Willing and able to provide written informed consent.

Subjects meeting any of the exclusion criteria at baseline will be excluded from study participation.

Exclusion Criteria are:

- Contraindication for estrogen use.
- Any medical condition that, in the opinion of the investigator, would place the subject at increased risk for participation.
- History of connective tissue disease
- Previous hysterectomy or pelvic organ prolapse surgery.
- Known allergic reaction to any agent under investigation or required by the protocol.
- Use of hormone therapy in postmenopausal women within the last 90 days.
- History of prior non-compliance or the presence or history of psychiatric condition (including drug or alcohol addiction) that would, in the opinion of the investigator, make it difficult for the subject to comply with the study procedures or follow the investigators instructions.
- Females who are pregnant or lactating.

